FAMS Mobile Health Intervention for Diabetes Self-care Support
NCT02481596
4-9-2018

NCT 02481596 - Statistical analysis plan

Targeted mediators were helpful family/friend involvement, and harmful family/friend involvement. The primary outcomes were dietary behavior and physical activity and the secondary outcome was diabetes self-efficacy. Analyses followed intention-to-treat principals. Regression models examine change in the outcome of interest adjusted for the baseline value of the outcome of interest with restricted cubic splines (three knots) to allow for a nonlinear effect of the baseline value. We ran separate models to examine the 3-month effects and the 6-month effects. Missing data were imputed using multiple imputation using chained equations to generate $m=20$ datasets. Between groups analysis compared improvements in the REACH+FAMS group to the control group on primary and secondary outcomes at 3- and 6-months.

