Given increased rates of T2DM-related complications and mortality among minority groups and patients with low SES [46, 47], it is particularly critical to focus family interventions on at-risk patient populations who may need more support to maintain self-care and glycemic control [48, 49]. Such populations have higher rates of limited health literacy [50], life stressors [51-53], and depression [54, 55], making them more vulnerable to the detrimental effects of obstructive family behaviors on self-care and A1C [48, 49]. Interventions simply educating and/or involving families without working to reduce obstructive family behaviors may actually evoke less patient adherence [56-59]. We explored cross-sectional associations between diabetes-specific supportive and obstructive family behaviors and adults' T2DM self-care behaviors and A1C in the target population and found that family members' supportive and obstructive behaviors were each independently associated with more and less adherence to self-care, respectively [56].

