**RANDOMIZATION - Describe the randomization process (who will randomize, how will randomization be determined, etc.)**

After completing informed consent and enrolling in the study, participants are randomized to one of three study groups: REACH, FAMS, or control (see Research Study Design). Randomization is determined with a statistical script developed in R, and run by a member of KSP. (This feature is not yet integrated into REDCap. Once available, this will occur in REDCap). Unblinded KSP calls each participant prior to the Sunday in which they will begin the program to communicate what they can expect based on their study group assignment (see REACH, FAMS, and Control Condition Explanations).

All participants will receive a welcome text message to begin the program (see Stand Alone Text Content). All participants will be provided with access to the REACH Helpline for technology-related (e.g., inquiries about sending or receiving text messages), research-related (e.g., inquiries about participant compensation), and medication-related (e.g., inquiries about medication side effects) questions (see Helpline Recording Script). The latter will be addressed by a clinical pharmacist on our team who can provide medication management support, if needed (see Clinic Helpline Agreements). All participants will also receive a text message notification when their A1c results are ready (see section below on Specimen Collection).

Participants assigned to REACH or FAMS will receive a one-way text message each day addressing individual barriers to medication adherence and medication regimen, diet, exercise, or self-monitoring of blood glucose (SMBG) (see REACH One Way SMS Content and FAMS Patient User SMS Content). Each day, they will also receive a two-way text message before bedtime that asks about their medication adherence that day (see Stand Alone Text Content). These daily responses are used to provide adherence feedback sent via one-way text message at the end of each week (See REACH Weekly SMS Feedback). Additionally, FAMS participants will receive a weekly two-way text message that solicits a response about their adherence to their diet/exercise goal for the week (see FAMS Weekly SMS Content). FAMS family member participants will receive one-way text messages 3-4 times per week, for up to six months (see FAMS Family Member SMS Content).

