**Date of IRB Approval: 04/09/2018**

**Institutional Review Board**

IRB-approved letter from [name] stating that research staff will contact them about the study unless they respond via e-mail or phone to opt-out. 7-10 days after the e-mails and letters are sent, KSP will call patients who did not opt-out to tell them about the study. We have approval to contact these patients from the Medical Director of Vanderbilt Primary care, and the primary care physicians at the clinics we are recruiting from.

Once enrolled, any participants randomized to FAMS will be asked if they want to invite an adult family member to participate. They can elect to invite a family member by providing the person's name and mobile phone number. KSP will then contact the family member to describe the study and formally invite them to participate (see also FAMS Recruitment and Enrollment Script Family Members).

Those participants who complete a follow-up survey electronically or via mailed paper copy will receive their materials along with a cover letter that explains the study components. KSP will fill out the information needed. Because this is a long study with several components, this letter and figure help to reiterate key points of the study, and we hope, also contribute to better retention. KSP will use to appropriate form based on how the participant will be completing the survey (e.g., online, mailed paper survey) and which items are needed for the timepoint (e.g., A1c, survey, both), fill it out with the applicable information, and these letters will be included when sending the online or paper follow-up survey materials.

**Identify the criteria for inclusion and exclusion and explain the procedures that will be used to determine eligibility. If psychiatric/psychological assessments will be conducted (e.g., depression or suicidal ideation screenings), state who will administer, his/her experience, and how risks will be managed.**

Patient inclusion criteria includes adults aged 18 years and older (per participant report and confirmed by a trained RA following informed consent); individuals with a diagnosis of T2DM; patient at a participating health center (Faith Family Medical Clinic, The Clinic at Mercury Courts, Vine Hill Community Clinic, Priest Lake Family & Women's Health Center, Neighborhood Health Clinics, and VUMC; see Faith Family, [name], and UCHS Letters of Support); and current treatment with oral and/or injectable daily diabetes medication.

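### The SAP model is valid but adjusts only for the outcome's own baseline; a short prespecified set of baseline covariates already collected would probably sharpen the FAMS estimate modestly

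*SAP*

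**What the plan says.** The SAP is a single paragraph. On the model it states that change in each outcome is "adjusted for the baseline value of the outcome of interest with restricted cubic splines (three knots"). No other covariate appears, and no reason is given for stopping there. On outcomes: "The primary outcomes were dietary behavior and physical activity and the secondary outcome was diabetes self-efficacy". On the family measures: "Targeted mediators were helpful family/friend involvement, and harmful family/friend involvement". On the contrast: "Between groups analysis compared improvements in the REACH+FAMS group to the control group on primary and secondary outcomes at 3- and 6-months". Missing values are filled by chained-equation imputation with 20 datasets, but the variables in the imputation model are not listed.

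The Protocol shows what else is known at baseline:

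- **Survey (Surveys, Interviews, and Questionnaires).** All patients complete a baseline survey, with a demographic section and a health-literacy measure. The instrument is an attachment that is not shown.
- **Clinic (Recruitment, inclusion criteria).** Being a patient at a participating site is an eligibility criterion. The list of sites ends with "Priest Lake Family & Women's Health Center, Neighborhood Health Clinics, and VUMC".
- **Prior evidence (Background).** In the target population, "family members' supportive and obstructive behaviors were each independently associated with more and less adherence to self-care".
- **Allocation (Randomization).** "Randomization is determined with a statistical script developed in R, and run by a member of KSP". No stratification or balancing variable is described.

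**The concern.** Baseline measures that predict later diet and activity reduce the residual variance, and so the standard error of the treatment contrast, when they are put in the model. Here most of them need no new data. Baseline diet, activity and self-efficacy must exist in every arm, because each serves as the baseline covariate in its own model, yet none is used in the models for the other two. Clinic is known for every patient. Helpful and harmful involvement are named as mediators, so baseline values are a strong inference, though the survey itself cannot be seen. The Background gives a substantive reason to expect the family measures to carry information about self-care.

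What is at stake is precision: somewhat wider intervals and somewhat lower power for the REACH+FAMS versus control contrast than the same patients could give. A second, conditional stake is that if the randomization script does balance on clinic or another prognostic variable, leaving that variable out of the model makes the intervals too wide. The documents do not say whether it does.

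**Working it through.** The documents state no power, SD, effect size or R-squared, so there is no figure of the plan's own to reproduce. The check asks how much a compact covariate set could change the standard error.

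**Inputs**

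- Accrual goal 525 (Protocol, Subject Population(s)) and three groups (Protocol, Randomization). *Assumed:* equal allocation, all 525 are patients, no loss to follow-up. This gives 525/3 = 175 per arm and N = 350 in the contrast.
- *Assumed:* baseline-to-follow-up correlation 0.5, linear on an SD scale.
- Added terms k = 5 for each primary outcome: the other primary outcome, self-efficacy, helpful involvement, harmful involvement, and clinic type (FQHC versus VUMC).
- *Assumed:* R², the share of the remaining variance that the added terms explain, from 0 to 10%.

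**Standard error of the stated model**

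SE = √(2(1 − 0.5²)/175) = 0.0926 SD. The 95% half-width is 1.96 × 0.0926 = 0.18 SD.

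**Effect of adding k terms**

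Variance ratio = (1 − R²) × (N − 5)/(N − 5 − k). The second factor is the price in degrees of freedom. For k = 5 it is 345/340 = 1.0147, and break-even R² = k/(N − 5) = 5/345 = 1.4%.

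| R² | Variance ratio | SE (SD) | Equivalent change per arm (175/ratio − 175) |
|---|---|---|---|
| 0 | 1.0147 | 0.0933 | −2.5 |
| 3% | 0.9843 | 0.0919 | +2.8 |
| 5% | 0.9640 | 0.0909 | +6.5 |
| 10% | 0.9132 | 0.0885 | +16.6 |

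**Why the set should be short**

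Break-even R² is 8/345 = 2.3% with eight added terms and 12/345 = 3.5% with twelve. Eight terms is the list above plus age, sex and health literacy. Twelve is the same list with five clinic indicators in place of one. At R² = 3%, twelve terms give 0.97 × 345/333 = 1.005, slightly worse than the SAP model.

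**Sensitivity to the assumptions**

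With 262 control and 131 FAMS patients (N = 393), break-even for five terms is 5/388 = 1.3%. With 140 per arm analysed (N = 280), it is 5/275 = 1.8%.

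**Check of the formula**

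A simulation with N = 350, nine added terms, no treatment effect and 4,000 runs per setting gave SE ratios of 1.009, 0.987, 0.969 and 0.905 at R² of 0, 5%, 10% and 20%. The formula gives 1.013, 0.988, 0.961 and 0.906. With the residual SD set to 1, the mean estimate lay within 0.0023 of zero under both models, so the two differ in precision and not in bias.

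**The case against.** The strongest reply is that nothing here is an error. Regressing change on baseline in a randomized comparison is valid, the outcome's own baseline is usually the best predictor and is already modelled flexibly, and no described stratification obliges clinic adjustment. The evidence in the Background is cross-sectional. It does not show that family behavior predicts later diet or activity once baseline diet or activity is in the model. All of this stands, and it is why the gain is a range that reaches down to a small loss.

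Three stronger readings are tempting, and the documents support none of them.

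- **That the adjustment is free.** No data collection is needed, but each term uses a degree of freedom, and a long list can lose precision, as the twelve-term case shows.
- **That chance imbalance in clinic mix passes directly into the estimate.** A lasting clinic difference is also present at baseline and is partly removed by the SAP model. Assume a VUMC share of 30% to 50%, so that the 95% range for the between-arm difference in share is 1.96 × √(2p(1 − p)/175), about 10 points. Assume also a clinic gap of 0.3 to 0.5 SD that is the same at both times. With a slope of 0.5, half the gap remains, and the shift is about 0.3 × 0.5 × 0.096 = 0.014 to 0.5 × 0.5 × 0.105 = 0.026 SD. This variation is already part of the standard error, and it is small beside the 0.18 SD half-width.
- **That the reported intervals are too wide.** This follows only if the randomization script balances on a prognostic variable. The Protocol does not say so, and the design attachment it cites is not shown.

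There is also a timing objection. The SAP is written in the past tense, although it is dated 4-9-2018 and the Protocol expects data collection to run to the end of 2019. If the models had already been run, new covariates could no longer be called prespecified. This stands as a condition on the fix.

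**Conclusion.** The point holds as a modest efficiency improvement, not as a validity defect. The SAP's estimate is likely, but not demonstrably, somewhat less precise than one that also uses baseline measures the trial already has. With about five added terms, the plausible gain is a 1% to 4% smaller standard error if they explain 3% to 10% of the remaining variance. The worst case is a loss of under 1%.

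The result rests on equal allocation of 525 patients, a correlation of 0.5, full follow-up and an R² that the documents do not supply. Baseline collection of the family measures in all arms is inferred, not stated.

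**What to change.** Before any outcome analysis, amend the model sentence so that each regression adjusts for the following, all fixed in advance:

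- the outcome's own baseline (three-knot spline, as now);
- the baselines of the other SAP outcomes among dietary behavior, physical activity and self-efficacy;
- baseline helpful and harmful family/friend involvement, if collected in all arms;
- clinic type, coded FQHC versus VUMC;
- any variable on which the randomization script balances. The SAP should state whether there is one.

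Only baseline values of the family measures may enter. Their post-baseline values are mediators, and adjusting for them would remove part of the effect being estimated.

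List the same variables in the imputation model, which is currently unspecified. Report the baseline-only model as a sensitivity analysis. If that model has already been run, keep it primary and label the adjusted model supplementary.

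The cost is a sentence or two in the SAP and about five degrees of freedom out of roughly 350. No new data are needed.

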**Institutional Review Board**

## Study Purpose and Description

**Provide a brief abstract of the study in lay language. The IRB Committees are comprised of scientists with varied backgrounds, non-scientists, and community members.**

This IRB application addresses the second of three aims for our overall research plan: to evaluate a mobile-phone delivered medication adherence intervention (called REACH; Rapid Education/Encouragement And Communications for Health) and test intervention effects on adherence and glycemic control among low income adults with type 2 diabetes mellitus (T2DM) receiving primary care at Federally Qualified Health Centers (FQHCs) or VUMC. In addition, family-focused components (called FAMS; Family-focused Add-on to Motivate Self-care) are integrated with the larger REACH intervention, and include diabetes coaching, goal-focused text messages delivered to the patient, and supplemental text messages delivered to an identified adult family member. We will evaluate the effects of the supplemental, family-focused intervention on family members' supportive and obstructive behaviors, patients' diabetes self-efficacy, and patients' adherence to diet and exercise. (Aim 1, to improve the content and functionality of an existing mobile phone-delivered medication adherence promotion intervention for consistency with the Information-Motivation-Behavioral skills model and clear health communication strategies, and test for usability and acceptability with patients, received approval [see IRB #140562] in April 2014.)

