**Institutional Review Board**

and homeless persons in the U.S. [69]. However, more research is needed to understand the health benefits of basic mobile phone interventions for racial/ethnic minorities and/or persons with low SES in general, particularly those persons with chronic conditions such as diabetes [70, 71] and the sustainability of such interventions in routine clinical care.

Therefore, we will test whether our intervention improves adherence-related information, motivation, and behavioral skills and whether improving these mechanisms drives improvements in adherence and, in turn, glycemic control. Intervention trials are notoriously concerned with establishing efficacy without understanding the mechanisms through which an intervention achieves its effect. The former is important for practice, but the latter tells us how to intervene more effectively, informing future research, practice, and policy [72, 73]. Our approach includes both; and for the latter, we will assess valid measures of adherence-related information, motivation, and behavioral skills to test (a) whether our intervention improved the IMB mechanisms; (b) whether such improvements are what produced improvements in adherence and, in turn, glycemic control; and (c) whether adherence improvements caused improvements in glycemic control.

We hypothesize that our SMS intervention will effectively improve medication adherence and glycemic control. We base this on our prior work and that of others. For instance, a 2012 study reported that patients with HIV who used an SMS intervention for 6 months were more optimally adherent even after intervention discontinuation [74]. In addition, in an SMS intervention with adults with T2DM, 100% of participants said they would recommend the program to family/friends with diabetes [75] and many actually did so [76], but to date no study has explored adult patients' receptivity to engaging their family members in SMS interventions about their own health and/or the potential benefits of doing so [77-79]. This is an important first step in expanding the reach of mHealth interventions to family members, who are at-risk for T2DM [80-82]. Rather than trying to change family members' behaviors directly, the supplemental family-focused intervention will target patients' ability to identify family behaviors that support or impede their self-care goals and enhance skills to ask for needed support and manage obstructive behaviors.

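### The SAP compares REACH+FAMS only with control, so it cannot show what the family-focused components add to REACH, although a REACH arm is randomised.

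*SAP*

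**What the plan says.** The SAP is one paragraph. Its only statement about which groups are compared is: "Between groups analysis compared improvements in the REACH+FAMS group to the control group on primary and secondary outcomes at 3- and 6-months". On outcomes it says: "The primary outcomes were dietary behavior and physical activity and the secondary outcome was diabetes self-efficacy". On mechanism it says: "Targeted mediators were helpful family/friend involvement, and harmful family/friend involvement". It describes no mediation model, three-arm model or comparison involving the REACH arm.

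The protocol describes the design as follows.

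- **Arms (Randomization section):** "participants are randomized to one of three study groups: REACH, FAMS, or control". The SAP's REACH+FAMS group is read here as the protocol's FAMS arm.
- **What FAMS is (Study Purpose and Description):** "family-focused components (called FAMS; Family-focused Add-on to Motivate Self-care) are integrated with the larger REACH intervention".
- **What is to be evaluated (same section):** "We will evaluate the effects of the supplemental, family-focused intervention on family members' supportive and obstructive behaviors", followed by "patients' diabetes self-efficacy, and patients' adherence to diet and exercise".
- **What FAMS is meant to change (Significance):** "the supplemental family-focused intervention will target patients' ability to identify family behaviors that support or impede their self-care goals".
- **What the active arms share (Randomization section):** both receive daily one-way texts, whose listed topics include diet and exercise, and a nightly text asking about medication taking.
- **What FAMS adds (Study Purpose and Description; Randomization; Surveys; Recruitment):** monthly telephone coaching, goal-related texts, and texts to a family member whom the patient may choose to invite.

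**The concern.** An add-on is normally judged by what it contributes beyond the thing it is added to. The planned contrast mixes that contribution with the effect of REACH itself. REACH cannot be presumed inert on the SAP's outcomes, because the daily texts described for both active arms list diet and exercise, the domains of both primary outcomes.

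The analysis as written can support a statement that the package beats control. It cannot tell a reader whether the coaching, goal texts and family-member texts made any difference beyond REACH. The randomised arm that could answer this goes unused in this analysis.

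A related gap is that the between-group sentence covers only primary and secondary outcomes. Family members' supportive and obstructive behaviours come first in the protocol's list of FAMS effects. They appear in the SAP only as mediators, with no stated group comparison.

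**Working it through.** **What the planned contrast estimates.** For any outcome at either time point:

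(REACH+FAMS − control) = (REACH − control) + (REACH+FAMS − REACH)

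The left side is what the SAP estimates. The last term is the increment from FAMS. The two differ by exactly the REACH effect, so they coincide only if REACH alone does nothing. The documents give no REACH effect for diet, physical activity or self-efficacy, so the difference cannot be computed from them.

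**What is missing.** The SAP has 2 primary outcomes, 1 secondary outcome and 2 mediators, at 2 time points: (2 + 1 + 2) × 2 = 10 possible REACH+FAMS versus REACH contrasts. None is specified.

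**How often the package contrast would be significant if FAMS added nothing.** There is no figure in the plan to reproduce, because the documents give no alpha, power, effect size, SD, allocation ratio or dropout rate. The following is an illustration.

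Inputs:
- The accrual goal is 525 (Protocol, Subject Population(s)). It is not stated how this divides between patients and family members.
- Assumed patients per arm, with equal arms: 525/3 = 175 at the upper end; 525/5 = 105, less 20% = 84, at the lower end. The lower end is a deliberately cautious choice with no source in the documents.
- Assumed correlation between baseline and follow-up: r = 0 to 0.5. Assumed test: two-sided 5%.
- Assumed REACH-only effect: d = 0.15 or 0.30 SD. FAMS increment: 0.

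Standard error in SD units: SE = √(1 − r²) × √(2/n).
- n = 175, r = 0.5: 0.866 × 0.1069 = 0.0926
- n = 84, r = 0: 1 × 0.1543 = 0.1543

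Chance of a significant favourable package result: 1 − Φ(1.96 − d/SE).

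| REACH-only effect | n = 84, r = 0 | n = 175, r = 0.5 |
|---|---|---|
| 0.15 SD | 0.162 | 0.367 |
| 0.30 SD | 0.494 | 0.900 |

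**Sensitivity to the split.** With no gain from baseline adjustment and 525 patients at 1:1:1, REACH-only effects of 0.1, 0.2 and 0.3 SD give 15%, 46% and 80%. At an assumed FAMS:REACH:control split of 1:2:3 the figures are 13%, 37% and 68%.

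**Precision of the missing contrast, under the equal-arm assumptions above.**
- Difference detectable with 80% power: 2.802 × SE = 0.259 to 0.432 SD.
- 95% confidence interval half-width: 1.96 × SE = 0.181 to 0.302 SD.

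**The case against.** Package versus control is a legitimate comparison, and the SAP labels the arm REACH+FAMS, so nobody is misled about what is estimated. The protocol names no comparator when it says the supplemental intervention will be evaluated, and nowhere states a hypothesis that FAMS improves on REACH. The REACH arm has its own purpose, medication adherence and glycaemic control. The SAP mentions neither, so it evidently does not cover the whole three-arm trial. The two text-content files are not shown, so it is unknown how much diet and exercise content REACH-only patients receive. The percentages rest on chosen inputs.

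Much of this stands. That the increment over REACH is intended is a reasonable inference from the words supplemental and add-on, not a stated estimand. The criticism is confined to this SAP, and the percentages show scale only. None of it changes the identity: the planned contrast contains the REACH effect, and no part of this SAP removes it. Naming mediators does not help, since no model is given, and mediation within REACH+FAMS versus control would not replace the randomised comparison with REACH.

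The added contrast has limits too. Because separate REACH and FAMS text files are cited, FAMS texts may replace some REACH texts. The contrast would then measure a swap plus an addition. Its imprecision also means that a null result could be misread as showing that FAMS adds nothing.

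**Conclusion.** The concern holds. The sole between-group contrast in the SAP estimates the package. It differs from the FAMS increment by the whole REACH effect, and none of the ten contrasts that would isolate the increment is specified. This conclusion needs only the identity and the text of the two documents, with the SAP's REACH+FAMS group taken to be the protocol's FAMS arm.

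The percentages depend on assumed arm sizes, correlation, significance level and REACH effects, and would change with them. The matter is worth fixing but does not invalidate the plan: the package estimate is sound for the question it answers. Confidence is moderate, because the protocol leaves the comparator for FAMS unstated.

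**What to change.** Fit the same baseline-spline models, with the same imputation procedure, to all three randomised arms. Add REACH+FAMS minus REACH at 3 and 6 months, with 95% confidence intervals, for diet, physical activity, self-efficacy, and helpful and harmful family/friend involvement. Take the involvement measures from the patient survey, since family members are invited only in the FAMS arm (Protocol, Recruitment).

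Keep REACH+FAMS minus control and confine its conclusions to the package. Let any statement about FAMS itself rest on the new contrast. Report it as a supporting estimate with its interval, and describe it as the difference made by the whole FAMS bundle. An interval that includes zero should not be read as evidence of no effect. If the contrasts are not added, restrict the FAMS objective and conclusions to the package.

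The cost is SAP wording and one more contrast per model; no new patients are needed. Ten comparisons are added (4 primary, 2 secondary, 4 mediator), the imputation must include the REACH arm, and the estimates may be imprecise and less favourable. The SAP is written in the past tense, so if analyses were already run the contrasts must be labelled as added later. The fix also assumes that the patient survey, which is not shown, asks about family/friend involvement in every arm. The Surveys section describes one schedule without distinguishing arms, but that does not settle the survey's content.
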